2.1 Objectives

2.1.1 Descriptive objectives

Regarding the patient and the disease

- To describe NSCLC patient characteristics.
 - Demographics.
 - o Co-morbidities and relevant medical history.
 - Disease-related habits.
- To describe the disease at baseline.
 - o Location, tumour type, stage, extent, mutation of biological markers.
 - o Related symptoms.
- To describe patient outcome.
 - Performance Status/ECOG.
 - Therapy outcomes and related events.
 - Disease progression.
 - o Death.

Protocol of Non-Interventional Study Drug Substance: N/A

NIS Code: NIS-ORU-IRE-2009/1

Version No: 4.0 Date: 8 December 2009

o Quality of life and functional status.

Regarding clinical management

- To describe hospital characteristics.
 - Size and type.
- To describe the diagnostic patterns of the disease.
 - Tests performed.
 - o Patient flow-chart until final diagnosis.
- To describe NSCLC treatment received.
 - o Surgery.
 - o Radiotherapy.
 - o Chemotherapy.
 - o Other.
- To describe any other use of health care resources.
 - Emergency visits.
 - Hospital stays.
 - Primary care visits.
 - Outpatient therapy.
 - Home care.

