4.1.1 Information regarding the patients and their disease

Patient Demographics and any other general patient information: Some of the study variables are considered as risk factors of disease progression and functional status therefore, in order to describe the study population, the following information will be collected:

- Gender.
- Date of birth.
- Ethnicity.
- Smoking habits.

[‡] When ICF is not required for medical record data collection

Protocol of Non-Interventional Study

Drug Substance: N/A

NIS Code: NIS-ORU-IRE-2009/1

Version No: 4.0 Date: 8 December 2009

Co-morbidities

Disease information: All aspects related with the disease.

- Disease stage and TNM classification. Only at first visit.
- Primary tumour location: Only at first visit.
- Histological classification and degree of differentiation. (Only at first visit).
- Extent of the disease.
- Related symptoms.
- Molecular biomarkers. (When available). Just to have information on whether such analyses were performed or not in real clinical practice.

Patient Evolution: All information on how the patient is progressing as regards the disease and on therapy-related factors.

- Performance Status (PS)/ECOG, including at diagnosis.
- Weight loss.
- Progression of disease. To be taken into account if disease progression is based on RECIST criteria and/or any other clinical assessment.
- Treatment response: Non-response, partial response, stable disease and complete response according to RECIST evaluation and/or any other clinical assessment.
- Death: Disease-related or for other reasons.
- Disease-related events: Any event the patient experiences that is related with the NSCLC condition (e.g. hospitalisation, primary care consultation, etc).
- Therapy-related events: Any event related to receiving NSCLC treatment (e.g. adverse events).

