4.1.2 Information regarding clinical management

Site description and characteristics: In order to describe the main characteristics of the sites providing health care for NSCLC patients. This variable will be not collected for each patient, but for each site involved in the study. This information will therefore be collected at the time of registering a participating site.

Type of hospital: Teaching hospital, research centre.

Protocol of Non-Interventional Study Drug Substance: N/A

NIS Code: NIS-ORU-IRE-2009/1

Version No: 4.0 Date: 8 December 2009

Diagnosis Procedures: This is one of the key factors in NSCLC patient management. These variables will allow us to determine how patients arrive at the department responsible of treating this type of patients, and how they have been managed during the period of time from the occurrence of the first symptom to the first therapy prescribed. Information will therefore be recorded regarding:

- Date of diagnosis.
- Disease-related triggering symptoms at diagnosis (Dyspnoea, Asthenia, Chest Pain, Cough, Dysphagia, Haemoptysis).
- Diagnostic technique(s).
- Date of first consultation about symptoms.
- Biomolecular determinations performed or not.
- Any other test performed for diagnostic purposes.

Therapy information: As with diagnosis, therapy is a key factor in terms of lung cancer patient management. The following variables will be collected to this end:

- Surgery: Performed or not and for explorative and/or resection purposes.
- Chemotherapy: onset date, end date, cycles, drug, best response and related adverse events when applicable. Any drugs involved in clinical research will be recorded as "clinical research drug" and onset date, end date and best response will be also collected.
- Radiotherapy. Onset date, end date, type, best response, and related adverse events.
- Other therapy received. Onset date, end date, type, best response and related adverse events. Also supportive care for anaemia should be included in this group: transfusions, erythropoetin, etc.

Use of health resources: This variable is closely related with the previous two, since diagnosis and therapy cover most of the time the patient is in contact with the professional responsible of treating this patients. All variables described above will be used to describe the use of health resources, and the following will also be collected:

- Date of each visit.

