4.4 Safety reporting

Due to the non-interventional character of a Non-Interventional Study, no pro-active safety data collection should take place. Only spontaneously mentioned safety events should be reported as required by the post-marketing pharmacovigilance regulations.

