6.2 Analysis of outcome variables in relation to objectives and hypotheses

Three groups will be created from baseline evaluation for the purpose of data analysis. The patients will be divided according to the baseline stage of their disease (non-advanced NSCLC patients, locally advanced NSCLC patients and metastatic NSCLC patients). For each of them the following variables will be considered:

- Clinical evolution from baseline to each visit:
 - o Changes in number of disease-related symptoms.
 - o Changes in the extent of the disease.
- Treatment response from baseline to each visit:
 - o Number of patients with complete response to treatment.
 - Number of patients with partial response to treatment.
 - Number of patients with stable disease under treatment.
 - o Number of patients with progression of disease after treatment.
 - O Progression-free time from the last progression or diagnosis to new progression of disease during the study period. The main analysis of the time to disease progression will be a Cox proportional hazards model to estimate the hazard ratio of progression among the analysis groups, with 95% confidence intervals. This will be a 2-sided test of the hypothesis, with a statistical significance level of 0.05. The assigned treatment will be included as a covariate.
- Treatment-related events.

Protocol of Non-Interventional Study

Drug Substance: N/A

NIS Code: NIS-ORU-IRE-2009/1

Version No: 4.0 Date: 8 December 2009

> o Mean number of patients with any treatment related event during the study period.

> o Mean number of patients with any serious treatment related event during the study period.

Mortality.

- o Number of patients with documented death during the study period.
- o Number of patients with a documented death due to NSCLC during the study period.

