It was also considered that the analytical objectives of the study would require multivariate analysis to determine the above sample size. This analysis will consider the main risk variables as independent variables. Based on the formula provided by Freeman²⁶ (the sample size must be 10 times the number of variables plus one) in order to perform such multivariate analysis, and having as variables for comparison: treatment, cycle, phase, primary tumour location, extent of disease, prior surgery, age, sex, EGFR markers, habits, PS/ECOG and type of hospital, the total sample size of 4,000 patients is advised.

Protocol of Non-Interventional Study Drug Substance: N/A

NIS Code: NIS-ORU-IRE-2009/1

Version No: 4.0 Date: 8 December 2009

A sample of 25% of patients per country will be included in the Quality of Life descriptive sub-study. Whether a sample from each site in the study is included in the sub-study will depend on the number of sites participating in each country. The number of sites involved will be determined bearing in mind that 25% of the total population included in the study must be invited to participate in the Quality of Life sub-study.

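### The protocol sets out to describe biomarker mutation and lists EGFR as a model variable, but Section 4 records only whether a biomarker test was done

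*Protocol*

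**What the plan says.** **Biomarkers.** The protocol summary and Section 2.1.1 list what is to be described about the disease at baseline: "Location, tumour type, stage, extent, mutation of biological markers". Section 6.4, in justifying the sample size for the multivariate analysis, ends its list of variables with "prior surgery, age, sex, EGFR markers, habits, PS/ECOG and type of hospital". On collection, Section 4.1.1 names molecular biomarkers, when available, and then states the purpose: "Just to have information on whether such analyses were performed or not in real clinical practice". Among the diagnostic procedures, Section 4.1.2 has "Biomolecular determinations performed or not".

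**Hospital.** Section 2.1.1 asks for both the size and the type of the hospital. The only site variable that Section 4.1.2 lists is "Type of hospital: Teaching hospital, research centre". Table 1 has a general row for site information.

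**Treatment-related events.** Section 4.1.1 lists therapy-related events, Section 4.1.2 lists adverse events under chemotherapy, radiotherapy and other therapy, and Table 1 marks adverse events due to therapy at each evaluation visit. Section 6.2 summarises them, including "Mean number of patients with any serious treatment related event during the study period", and Section 6.3 models them as an outcome. Section 4.4 says that "no pro-active safety data collection should take place" and that only events mentioned spontaneously are reported, as pharmacovigilance rules require.

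**The concern.** An objective can be met only if the variable that answers it is collected. A field showing whether a test was done gives the frequency of testing. It carries no information on what the test found, so the distribution of mutations cannot be derived from it. A later statistical analysis plan cannot repair this, because it cannot analyse a result that was never recorded.

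The same gap changes the meaning of the EGFR variable in the multivariate analysis. With these data it can enter a model only as tested versus not tested, and so cannot adjust for mutation status. This bears on the comparisons between treatments for which Section 6.3 promises P-values, since Section 1.1 names EGFR inhibitors among the options for recurrent disease.

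The hospital and safety passages raise smaller questions of the same kind: whether the variables and collection rules in Section 4 match what Sections 2 and 6 say will be described and analysed.

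**Working it through.** There is no plan figure to reproduce. The check sets the passages side by side, with one calculation to see whether the sample size depends on the EGFR variable.

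| Item | Needed by | Collected under | Match |
|---|---|---|---|
| Biomarker mutation | 2.1.1, baseline disease description | 4.1.1 and 4.1.2: test performed or not | No |
| EGFR markers | 6.4, variable list | 4.1.1 and 4.1.2: test performed or not | Only as testing status |
| Hospital type | 2.1.1; 6.4, variable list | 4.1.2 | Yes |
| Hospital size | 2.1.1 | Not listed in 4.1.2; Table 1 says only site information | Not stated |
| Treatment-related events | 6.2, 6.3 | 4.1.1, 4.1.2, Table 1 | Yes, but the scope of 4.4 is unclear |

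**Step 1, biomarkers.** The availability note in Section 4.1.1 might suggest that results are taken where they exist. The sentence after it closes that reading by confining the purpose to whether the analysis was done. Section 4.1.2 says the same independently, and Table 1 has no row for a result. The restriction is therefore explicit and stated twice, so it is not a mere omission.

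**Step 2, extent.** The baseline disease bullet in Section 2.1.1 names five items: location, tumour type, stage, extent and mutation. One of the five cannot be described. Section 6.4 lists treatment, cycle, phase, primary tumour location, extent of disease, prior surgery, age, sex, EGFR markers, habits, PS/ECOG and type of hospital, which makes 12. One of the 12 is limited to testing status.

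**Step 3, sample size.** Section 6.4 cites a rule of ten times the number of variables plus one. With 12 variables this gives 10 × (12 + 1) = 130, or 10 × 12 + 1 = 121 on the other reading. Without EGFR markers, 11 variables give 10 × (11 + 1) = 120, or 10 × 11 + 1 = 111. All four are far below the 4,000 patients stated, so the planned size does not depend on this variable.

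**Step 4, hospital size.** It is named in the objective and absent from the listed site variables. The site form may hold it under the Table 1 heading, but the protocol does not say so.

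**Step 5, treatment-related events.** Three places list them for collection and two analyse them. Section 4.4 taken alone points the other way. Its heading and its reference to pharmacovigilance rules suggest that it concerns reporting to authorities, but its opening sentence carries no such limit.

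**The case against.** The overall aim in Section 2 is to describe clinical management, and for that aim whether testing was done is itself a useful variable. Section 4.1.1 states that purpose deliberately. EGFR markers appear in a sample-size argument, whereas Section 6.3 names stage, histology and PS as examples of characteristics and does not mention EGFR. The variable in Section 6.4 could therefore be read as testing status. This stands as far as it goes, and it is why narrowing the objective is as valid a remedy as adding a field. It does not rescue the mutation item in Section 2.1.1, which testing status cannot answer.

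Some stronger readings are tempting, and the document does not support them:

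- **Section 4.4 leaves an analysed outcome uncollected.** Sections 4.1.1 and 4.1.2 and Table 1 all list treatment-related events, and Section 3.1 makes the medical record the data source. What remains is a sentence of unclear scope. That event rates would differ by site because of it is conjecture.
- **Section 6.4 allocates the sample by hospital size.** The remark about large teaching hospitals is a conditional illustration of representativeness and sets no allocation.
- **Some hospitals fit no category.** The two hospital types named are not shown to be a closed response list, and the site form is not available.
- **The EGFR variable would be mistaken for mutation status.** Nothing in the protocol shows this.
- **The count of serious events is defective.** The definition of serious and the form of the summary can be settled in the analysis plan, the case report form or the instruction manual promised in Section 5.1.

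**Conclusion.** The inconsistency on biomarkers is real and should be fixed. As the protocol stands, no biomarker result is listed for collection for any patient, the mutation part of the baseline objective cannot be answered, and EGFR can be analysed only as tested or not tested. This rests on reading Sections 4.1.1 and 4.1.2 as they are worded. If the case report form already holds results, the protocol text is what needs correcting.

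The effect is confined to one descriptive item and one of the 12 listed variables. A reader might infer that the main analyses or the sample size are compromised. They are not: the response, progression and mortality endpoints do not depend on this field, and the 4,000 figure does not come from it.

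The hospital-size gap and the scope of Section 4.4 are minor clarifications. Size is one value per site that can be obtained at any time, and treatment-related events are already listed for collection.

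**What to change.** **Main change, one of two.** (1) In Sections 4.1.1 and 4.1.2, record for each biomarker the result where a test was done and its result is in the medical record: mutated, wild type, not evaluable or not tested. (2) Otherwise, narrow the objective in Section 2.1.1 and the protocol summary, and the variable in Section 6.4, to testing status.

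The first option costs one eCRF field per biomarker and no additional test or visit. Results may be incomplete for patients diagnosed elsewhere, although Section 3.1 makes full access to the record a condition of including them. The second option costs only wording, and gives up any description of mutation.

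**Minor changes.** Add hospital size to the site variables in Section 4.1.2, at one field per site. Reconcile Section 4.4 with Table 1 and Sections 4.1.1 and 4.1.2 by stating whether it governs only pharmacovigilance reporting, so that it is clear how treatment-related events reach the analyses in Sections 6.2 and 6.3. That is a change of wording.

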4.1.2 Information regarding clinical management

Site description and characteristics: In order to describe the main characteristics of the sites providing health care for NSCLC patients. This variable will be not collected for each patient, but for each site involved in the study. This information will therefore be collected at the time of registering a participating site.

Type of hospital: Teaching hospital, research centre.

Protocol of Non-Interventional Study Drug Substance: N/A

NIS Code: NIS-ORU-IRE-2009/1

Version No: 4.0 Date: 8 December 2009

Diagnosis Procedures: This is one of the key factors in NSCLC patient management. These variables will allow us to determine how patients arrive at the department responsible of treating this type of patients, and how they have been managed during the period of time from the occurrence of the first symptom to the first therapy prescribed. Information will therefore be recorded regarding:

- Date of diagnosis.
- Disease-related triggering symptoms at diagnosis (Dyspnoea, Asthenia, Chest Pain, Cough, Dysphagia, Haemoptysis).
- Diagnostic technique(s).
- Date of first consultation about symptoms.
- Biomolecular determinations performed or not.
- Any other test performed for diagnostic purposes.

Therapy information: As with diagnosis, therapy is a key factor in terms of lung cancer patient management. The following variables will be collected to this end:

- Surgery: Performed or not and for explorative and/or resection purposes.
- Chemotherapy: onset date, end date, cycles, drug, best response and related adverse events when applicable. Any drugs involved in clinical research will be recorded as "clinical research drug" and onset date, end date and best response will be also collected.
- Radiotherapy. Onset date, end date, type, best response, and related adverse events.
- Other therapy received. Onset date, end date, type, best response and related adverse events. Also supportive care for anaemia should be included in this group: transfusions, erythropoetin, etc.

Use of health resources: This variable is closely related with the previous two, since diagnosis and therapy cover most of the time the patient is in contact with the professional responsible of treating this patients. All variables described above will be used to describe the use of health resources, and the following will also be collected:

- Date of each visit.
- Type of visit: scheduled (for treatment, clinical assessment or both) or non-scheduled.
- Departments visited until referral to the responsible department of treating this type of patients.

Protocol of Non-Interventional Study Drug Substance: N/A

NIS Code: NIS-ORU-IRE-2009/1

Version No: 4.0 Date: 8 December 2009

- Tests performed (excluding those reported in the diagnosis).
- Length of hospital stay (if applicable), reason for hospitalisation.
- ICU/ER visits.
- Any other specialist visits.
- Any other disease-related health professional visits.

4.1.3 Patient Reported Outcomes (PROs)

Patient Reported Outcomes play a particular role in this study. They will be measured in a sample (25% of the whole sample) of consenting patients at a limited number of sites per country. The sample will include patients at different stages of the disease during the study period who have received different treatment regimens. It is assumed that there will be a representative sample of advanced stage patients.

Each participating country will endeavour to include patients in the PRO sample bearing in mind that the sample must be representative of the whole study population.

Only patients who are not participating in clinical trials will be asked to participate in the Quality of Life sub-study.

- FACT Questionnaires¹⁹: These are a series of instruments designed to be sensitive to changes in cancer patients. They contain questions designed to measure SWB and EWB as well as PWB and FWB and are simple to use and score. The FACT-L subscale enables the assessment of disease-related symptoms associated with lung cancer.
- EUROQoL/EQ-5D²⁵: This is a standardised instrument for use as a measure of health outcome. Applicable to a wide range of health conditions and treatments, it provides a simple descriptive profile and a single index value for health status.

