3. STUDY PLAN AND PROCEDURES

3.1 Overall study design and flow chart

This is a multinational, multicentre, non-interventional, prospective cohort study to be carried out in a representative selection of hospitals in order to assess lung cancer management in countries throughout Central Eastern Europe and Russia. Within the scope of this study, no diagnostic or monitoring procedures in addition to the routine procedure will be applied to the patients.

To ensure a valid picture of real life management, sites will be selected focusing on representative hospitals where lung cancer patients are being managed, in all participating countries.

All NSCLC patients attending the responsible department of treating this type of patients (e.g. Oncology Department, Pulmonology Department) for the first time (regardless of whether the patient is diagnosed with locally, advanced or metastatic disease) at the participating sites from the first of January 2010 to the end of July 2010. Patients diagnosed, or even treated, in other departments within the same hospital or in another hospital are susceptible to be included in the study if full access to the patient's medical record is made available.

Patients could be retrospectively included in case of not receiving the Ethics Committee approval by the first of January 2010, but only those patients attending for the first time during the enrolment period.

Information regarding patient and disease characteristics will be taken from the medical record, as well as management approaches regarding the visit plan, diagnostic tests performed and therapies received by the patient.

A sample of patients will be invited to complete Quality of Life questionnaires when coming to the responsible department of treating this type of patients for assessment. PROs will be collected at each evaluation visit from the first visit (diagnosis) to last visit (after 12 months). PROs will not be completed at treatment administration visits and/or disease- or treatment-related event visits.

The data source for this study will be the medical record at the responsible department of treating this type of patients for each patient. Neither visits nor interventions will be carried out for the study purposes.

Protocol of Non-Interventional Study Drug Substance: N/A

NIS Code: NIS-ORU-IRE-2009/1

Version No: 4.0 Date: 8 December 2009

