3.3.2.1 Inclusion Criteria

For inclusion in the study, patients must meet all of the following criteria:

- 1. Confirmed NSCLC diagnosis (e.g. bronchoscopic biopsy or FNAB), all stages, men and women, attending the responsible department of treating this type of patients for the first time between January 1st, 2010 and August 1st, 2010.
- 2. For PRO sub-sample: ability to read and write since they will be asked to participate in the PRO part of the study. Selection will not be based on the disease stage of each patient, in order to avoid a selection bias.
- 3. 18 years of age or more.

-

[†] Only when required by local authorities.

Version No: 4.0

Date: 8 December 2009

3.3.2.2 **Exclusion Criteria**

According to the study design there will not be any exclusion criteria in order to provide a high external validity and to obtain the most accurate real daily practice information.

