7. STUDY MANAGEMENT

7.1 Monitoring and Quality Control

Before the first patient is recruited into the study, the local AstraZeneca MC representative or delegate will:

- Establish the adequacy of the facilities and the investigator's capability to appropriately select the sample.
- Discuss with the investigator(s) (and other personnel involved in the study) their responsibilities with regards to protocol compliance, and the responsibilities of AstraZeneca or its representatives. This will be documented in a Study Agreement between AstraZeneca/delegate and the investigator.

During the study the local MC representative or delegate may implement several activities to assure compliance with AZ standards of quality. These activities could include but are not limited to:

- Contacts with the sites to:
 - Provide information and support to the investigator(s),
 - Confirm that the investigational team is complying with the protocol and data are being accurately recorded in the electronic case report forms (eCRFs).
 - Ensure that the informed consent form is signed and stored at the investigator's site (only if required, see above).
- Monitoring activities for:
 - Checking a sample of ICFs (only if required).
 - Checking that patients exist by reviewing the existence of their medical records (a sample).
 - Different signals (e.g., high rejection rate in a site) should be used as possible triggers for low protocol compliance by investigators. Low rate of NSCLC patients (number of NSCLC identified patients/total number of patients

Version No: 4.0 Date: 8 December 2009

attending the clinic) in the identification period, compared with the expected prevalence.

If these, or any other signal occurs or if the local coordinator is suspicious of a potential non-optimal level of protocol compliance by the site investigator, specific measures should be adopted to evaluate the situation, identify the issue and implement specific action plans to correct the situation. These mechanisms should be agreed with the Steering Committee.

In a random sample of sites (10% in each country), a qualified, trained individual other than the Principal Investigator (preferably a CRA) should monitor all the patients included in the study at the selected sites (in terms of ICF collection). This procedure should be performed after 50% of the expected sample is already included.

7.2 **Training of staff**

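### The 25% quality-of-life sample must be representative, but no rule fixes which sites or patients enter it, and the 25% is defined in two ways

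*Protocol*

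**What the plan says.** Section 4.1.3 describes the PRO sample in four statements.

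- Setting: "They will be measured in a sample (25% of the whole sample) of consenting patients at a limited number of sites per country".
- Make-up: "The sample will include patients at different stages of the disease during the study period who have received different treatment regimens".
- Advanced disease: "It is assumed that there will be a representative sample of advanced stage patients".
- Method: "Each participating country will endeavour to include patients in the PRO sample bearing in mind that the sample must be representative" of the full study population.

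On who may be chosen, Section 3.3.2.1 (criterion 2) requires PRO patients to be able to read and write and adds: "Selection will not be based on the disease stage of each patient, in order to avoid a selection bias". Sections 3.3.2 and 4.1.3 restrict the sub-study to patients who are not in clinical trials.

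On the target, Section 6.4 first says that a quarter of patients in each country will be included. It then says that "25% of the total population included in the study must be invited to participate". It leaves the involvement of sites to depend on how many sites a country has.

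For the main cohort there is a rule: Section 3.3.1 tells each investigator to invite every new patient who meets the criteria.

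**The concern.** A sample is representative because of how it was drawn. Here the requirement is stated and the drawing is not: countries are asked to try, and for advanced stages the result is assumed. Barring selection on stage removes one strong prognostic factor. Performance status, weight loss, co-morbidity and general fitness within a stage remain open, and these bear on both quality of life and the ability to complete questionnaires. If fitter patients are approached more often, baseline scores will tend to look too good and decline too small.

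All FACT-L and EQ-5D results rest on this sample. Section 2.1.2 makes factors associated with quality of life an analytical objective, Section 6.3 marks two of the PRO change analyses as of particular interest, and Section 3.2 treats freedom from selection bias as essential.

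The point belongs in the protocol. Enrolment ends on 1 August 2010, while Section 6.1 requires the SAP only before database lock, planned for 1 October 2011. An analysis plan cannot restore invitations that were not made or reasons that were not recorded.

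**Working it through.** The protocol derives no sample size or precision for the PRO part, so there is no figure of its own to reproduce beyond the 25%. The check is mainly a comparison of sections.

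**1. Is there a selection rule anywhere?**

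- Section 3.3.1: invite all, but for the main study only.
- Section 3.3.2: a quarter of patients will be asked; it does not say by whom or how they are chosen.
- Section 4.1.3: a limited number of sites, with no criterion for which.
- Section 6.4: can be read as choosing enough sites to yield 25%, but it also contemplates sampling within sites. Neither is fixed.
- Section 7.1: the sponsor's representative is to "Establish the adequacy of the facilities and the investigator's capability to appropriately select the sample". This concerns the study in general and gives no PRO rule.
- Section 4.3.1: unspecified steps against bias, in the text on administering questionnaires.
- Section 4.2: a log with reasons for non-inclusion in the study, not for being left out of the PRO part.

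No random, consecutive or every-k-th rule exists at site or patient level.

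**2. When is PRO membership settled?** Section 3.1: "PROs will be collected at each evaluation visit from the first visit (diagnosis) to last visit (after 12 months". Table 1 marks PROs at the inclusion assessment, and the Summary has questionnaires collected straight after consent. Entry is at baseline. The make-up sentence in Section 4.1.3, which refers to regimens received, can therefore only describe what is expected, apart from treatment given elsewhere before entry.

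**3. What does 25% mean?** Inputs: 4,000 patients overall (Section 6.4), 500 in Russia (Summary), and a consent rate of 60% to 80% (assumption; the protocol gives none).

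- As included: 0.25 × 4,000 = 1,000; Russia 0.25 × 500 = 125.
- As invited: 1,000 × 0.60 = 600 to 1,000 × 0.80 = 800; Russia 125 × 0.60 = 75 to 125 × 0.80 = 100.

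**4. How much of the cohort can be asked?** Section 6.4 gives 80–90% at stage IIIb/IV, 75–80% of these treated, and about 33% of the treated on investigational products.

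- Low: 0.80 × 0.75 × 0.33 = 19.8%. High: 0.90 × 0.80 × 0.33 = 23.8%.
- If all of these are trial participants and known as such at invitation (assumption), 76.2% to 80.2% of the cohort can be asked, before the literacy requirement.
- Inviting 25% of the cohort then means inviting 0.25/0.802 = 31.2% to 0.25/0.762 = 32.8% of those who can be asked.

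**5. Illustration of selection, not an estimate.** Section 1.1 gives 35% one-year survival in stage IIIB/IV. If one-year survivors were r times as likely to be invited, their share of the advanced-stage sample would be 0.35r/(0.35r + 0.65): 44.7% at r = 1.5 and 51.9% at r = 2. Both values of r are assumed, and an inviter cannot observe future survival, only fitness. The formula does not contain the sample size, so more patients would not reduce the shift.

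**The case against.** The strongest reply is that nothing shows the sample to be badly chosen. A reader might infer that clinicians hand-pick PRO patients. The documents do not say so: Section 3.3.2 says only that patients will be asked, and Section 6.4 may mean that whole sites are selected. This stands. Convenience selection is permitted, not prescribed.

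A reader might also infer that the sample will be filled later by regimen, which would favour patients who survive to later lines. Step 2 of the working rules that out as a plan.

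Nor does a mix of stages contradict Section 3.3.2.1. A sample not selected on stage will ordinarily contain several stages, and that section is a genuine safeguard.

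It would also go too far to call the 95% intervals void, or to claim that within-site randomisation would make them valid for all NSCLC patients. Sites for the whole study are chosen purposively for representativeness (Sections 3.1 and 6.4), so the gain from a rule is representativeness of the cohort at hand. Section 6.4 calls the sub-study descriptive, and selection that acts equally across treatments need not bias treatment differences. No differential mechanism is documented.

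What remains is the absence of a rule. Sections 3.3.2.1, 4.2 and 4.3.1 do not supply one.

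**Conclusion.** The point holds as a gap in design. Sections 4.1.3 and 6.4 require a representative PRO sample but fix neither which sites nor which patients enter it, and the only bar is on disease stage. Selection on performance status or fitness within stage stays open. It would bias the FACT-L and EQ-5D descriptions and weaken their extension to the cohort.

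The protocol gives no basis for the size of that bias. The survival shares in the working depend entirely on the assumed r.

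Two smaller defects can be sized. Reading the 25% as invited instead of included lowers the yield from 1,000 to between 600 and 800 if consent is 60–80%. The exclusion of trial participants puts about 20–24% of the cohort out of reach on Section 6.4's own shares, if those on investigational products are all in trials. The sample cannot then represent the whole study population as Section 4.1.3 requires.

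**What to change.** Amend Sections 4.1.3 and 6.4 as follows.

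1. State that PRO invitation is set at registration, before the first questionnaire and without clinician choice, among patients eligible for the PRO part. Use either a random flag from the eCRF or the local coordinator's list, or invitation of all consecutive eligible patients at PRO sites drawn to give 25% of expected enrolment. Set the flag probability with the restricted frame in mind: about 31–33% of eligible patients if all sites take part, and higher within sites if only some do.
2. Reword the sentence on treatment regimens as the expected make-up, not a selection criterion.
3. Use one definition throughout: 25% invited.
4. Keep a PRO-specific log of patients invited, declining and not asked, with reasons. Compare invited, consenting and other patients on the baseline data that Section 4.1.1 already collects.
5. State that representativeness is limited to patients who are not in clinical trials.

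The cost is protocol wording, one flag or list, and a short log, with no extra patients or visits. The downside is that some invited patients will decline or be unable to complete the questionnaires, so the completed share may fall below 25%.
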